#### **Primary safety endpoint**

The primary safety endpoint of this study will be the incidence of composite Major Adverse Events (MAE) at 30 days following stenting of an obstruction in the iliofemoral venous segment. MAEs will be adjudicated by a Clinical Events Committee (CEC), except for stent thrombosis and stent migration as they are confirmed by core laboratory.

The components of the 30-day MAE composite include:

- All-cause death occurring post-procedure
- Clinically significant (i.e. symptomatic, confirmed by CT pulmonary angiography) pulmonary embolism
- Major bleeding complication (procedural)
- Stent thrombosis confirmed by imaging as assessed by core laboratory
- Stent migration confirmed by imaging as assessed by core laboratory

Note: Migration excludes stent dislodgement at the index procedure as may occur with under-sizing of a stent.

---

All subjects will undergo DUS assessments for determination of patency.

An additional venogram must be performed when:

(1) DUS assessment is suggestive of ≥50% restenosis or occlusion per investigator assessment, or  
(2) when DUS is non-diagnostic or suboptimal such as when a patient is obese (e.g. with a BMI >40), or  
(3) is clinically required, or in other words when the patient is having symptoms of venous disease in the target limb requiring a venogram.

All DUS and venographic imaging examinations will be analyzed by respective independent core laboratories.

Clinically driven is defined as the recurrence of symptoms present at baseline or the onset of new symptoms including, but not limited to venous pain, swelling, dermatitis, or ulceration related to the target limb.

Clinically driven target lesion revascularization will be adjudicated by the CEC based on core laboratory adjudicated imaging data and relevant clinical information provided by the site.

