**Note: If core laboratory is unable to assess the venographic evidence, site reported data will be used.**

- 4. Primary Patency at 24- and 36 months:** Freedom from occlusion of the stented segment of the target lesion, freedom from restenosis ≥50% of the stented segment, and freedom from clinically driven target lesion revascularization (CD-TLR).
- 5. Primary Assisted Patency at 12-, 24- and 36 months:** Uninterrupted patency of the stented segment of the target lesion with a secondary intervention, also known as an adjunctive treatment (e.g. balloon venoplasty, subsequent stenting, etc.).
- 6. Secondary Patency at 12-, 24-, and 36 months:** Patency of the stented segment of the target lesion after subsequent intervention for an occlusion.
- 7. Target Lesion Revascularization (TLR) through 30 days, 6-, 12-, 24- and 36 months:** Any re-intervention of the stented segment of the target lesion.
- 8. Major Adverse Events (MAE) through 6-, 12-, 24- and 36 months:**  
MAEs include:
  - All-cause death occurring post-procedure
  - Clinically significant (i.e. symptomatic, confirmed by CT pulmonary angiography) pulmonary embolism
  - Major bleeding complication (post-procedural)
  - Stent thrombosis confirmed by imaging as assessed by core laboratory
  - Stent migration confirmed by imaging as assessed by core laboratory

**Note:** Migration excludes stent dislodgement at the index procedure as may occur with under-sizing of a stent

All MAEs will be adjudicated by a CEC, except stent thrombosis and stent migration which are confirmed by the core laboratory.

---

 Confirmed by Duplex ultrasound scan evaluated by independent core laboratory. In cases where both DUS and venography were used at the same time point, venography would be used for the primary assessment.

[figure not shown]
**9. Delayed Stent Migration at 12-, 24-, and 36 months:** position change of a venous stent observed with an imaging modality > 1 cm from its original location at the conclusion of the index procedure, as determined with regard to a reference anatomic structure.

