### **Safety Outcomes**

Adverse events were generally tabulated as periprocedural ( $\leq 30$  days) or later. This review focused on those events that occurred within 30 days of the index procedure. The following occurrences were tabulated: periprocedural ( $\leq 30$  day) death, major hemorrhage (using the Bleeding Academic Research Consortium, or BARC definition; Types 3a or greater), clinically-evident pulmonary embolism, and access site complications (wound hematoma, false aneurysm and arteriovenous fistula).

The findings suggested that periprocedural death and pulmonary embolism were exceedingly uncommon in the patient populations studied; each occurring in fewer than 1% of patients treated (**Table X** and **Table XI**). The most common events were wound hematoma, stent thrombosis, and stent dislodgement/migration. Major hemorrhagic complications (BARC Type 3a or greater) occurred in approximately 1.1% of patients.

It was often impossible to determine whether major hemorrhagic complications occurred as a result of pharmacologic thrombolytic therapy in those series in which it was employed, accounting for a higher frequency of hemorrhagic complications in series that included patients with acute venous thromboses. Similar findings were evident for wound hematomas. Early ( $<30$  day) stent thrombosis was more common in post-thrombotic cases (4.9%) and was rare in non-thrombotic cases (0.2%). In this literature review, loss of stent patency within 30 days was synonymous with stent thrombosis; no effort was made to differentiate different thrombosis from other causes of occlusion since few publications specified the etiology of the process. Stent migration (exclusive of dislodgement) occurred more often in acute (2.4%) and non-thrombotic cases (2.0%) compared with the other groups (0.8%), possibly related to the absence of chronic stenotic disease in these cohorts; where chronic stenoses may have protective effects on the

 Percentages refer to the number of series that reported use of a particular stent. Percentages add to more than 100 since many series used more than a single type of stent.

 Dislodgement is defined as stent displacement from the initial deployment site due to catheter/wire/balloon manipulations at the index procedure.

stability of a stent. Neither stent migration or stent dislodgement was reported in any of the post-thrombotic cases.

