**Table XII. Complications through 12 months**

Clinical Category	Target Lesion Revascularization	Stent Fracture	Stent Migration 
Acute	4.8%	0.0%	2.4%
Post-thrombotic	13.0%	0.0%	0.0%
Non-thrombotic	Not Specified	0.0%	2.0%
Mixed, Acute & Chronic	7.0%	5.3%	Not Specified
Mixed; PT and NT	4.5%	Not Specified	1.1%
All Stent Publications	8.3%	1.4%	1.6%

 The actual weighted average is 0.03%.

 Where specified, stent migration included only those events occurring after the index procedure. Stent movement occurring during the index procedure is tabulated as "stent dislodgement" in Table XI.

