Stent migration	
Stent migration (as part of primary safety and secondary MAE endpoints): position change of a properly sized venous stent observed with an imaging modality, with displacement of the stent outside of the intended treatment segment after the conclusion of the index procedure, as determined with regard to a reference anatomic structure.
 
Delayed stent migration (as part of secondary endpoint): position change of a venous stent observed with an imaging modality > 1 cm from its original location at the conclusion of the index procedure, as determined with regard to a reference anatomic structure.
 
Stent migration occurs following the proper deployment of a venous stent after the index procedure (i.e. stent movement or dislodgement during the index procedure will not be noted as stent migration).

Stent thrombosis	
Occlusion of the stented venous segment occurring at any time following stent placement.
 
Stent thrombosis may be diagnosed by Duplex Ultrasound. It needs to be confirmed by venogram or IVUS.

Thrombosis	
A total occlusion due to thrombus formation as confirmed by sudden onset of symptoms and documented by DUS and venogram and/or IVUS at the target vessel.

Vein compression syndrome	
A condition in which compression of the common iliac venous outflow tract of the left lower extremity may cause discomfort, swelling, pain, or blood clots

	(deep vein thrombosis) in the iliofemoral vein (also known as the May-Thurner syndrome).
Venous occlusive disease	Any pathologic process that occurs from underlying stenosis or occlusion of the veins.

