**Table 3. Individual Component Event Determination For 30-Day Safety Endpoint**

Primary Safety Endpoint Component Events	Data Source	Event Failure	Individual Endpoint Derivation Rules	Composite Endpoint Derivation Rules
All-cause death	CEC	Event within 30 days post-index procedure by CEC adjudication	Numerator: event-specific, e.g. number of subjects with all-cause death within 30-day post index procedure, will be the numerator for 30-day all-cause death event rate calculation; Denominator: event specific denominator includes any subjects with the event, or subjects had no event but had at least 23-day of clinical follow-up	Numerator: number of subjects with at least one of these five events within 30 days post-index procedure; Denominator: evaluable subjects – any subjects with at least one of these five events, or subjects had none of these five events but had at least 23-day of clinical follow-up
Clinically significant pulmonary embolism	CEC			
Major bleeding complication (procedural)	CEC			
Stent thrombosis	Imaging-Confirmed	Stent thrombosis or migration within 30 days post index-procedure, confirmed by Venogram imaging		
Stent migration	Imaging-Confirmed			

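### Protocol Appendix B counts migration in the MAE endpoints only for a *properly sized* stent, an undefined condition that the endpoint sections, SAP Table 3 and the literature review do not state

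*Protocol*

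**What the plan says.** The Appendix B entry for stent migration has two definitions and a closing sentence.

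- The definition that feeds the primary safety and secondary MAE endpoints reads "position change of a properly sized venous stent observed with an imaging modality". It further requires that the stent has left the segment meant to be treated, once the index procedure is over.
- The delayed-migration definition, used only for a secondary endpoint and repeated in Protocol section 6.3.2, reads "position change of a venous stent observed with an imaging modality > 1 cm from its original location at the conclusion of the index procedure". It has no size condition.
- The closing sentence takes movement during the index procedure out of both.

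The other places that govern the MAE component are these.

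- **Protocol section 6.3.1:** "Migration excludes stent dislodgement at the index procedure as may occur with under-sizing of a stent". Section 6.3.2 and SAP sections 7.9.2 and 7.9.3 carry the same note. It is the only exclusion they state.
- **SAP Table 3**, which sets how each component is determined: "Stent thrombosis or migration within 30 days post index-procedure, confirmed by Venogram imaging". Its conditions are timing and imaging, not size.
- **Protocol Appendix A**, the source of the 5.6% expected rate and the 12.5% goal, sets apart only index-procedure movement. "Dislodgement is defined as stent displacement from the initial deployment site due to catheter/wire/balloon manipulations at the index procedure". A footnote to its Table XII adds: "Where specified, stent migration included only those events occurring after the index procedure".

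Protocol section 10.5.7 recommends a stent diameter relative to the reference vessel, allows that reference to be obtained in several ways, and says that good sizing reduces migration. Neither document links that section to the endpoint definition.

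**The concern.** Index-procedure movement is already excluded by the closing sentence of the Appendix B entry. The only further thing the size condition can do is remove movement that happens after the procedure. By the Protocol's own statement in section 10.5.7, the stents it would remove are the ones more prone to migrate, so any effect would favour the device.

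The condition also has no stated criterion, assessor or timing. Migration is confirmed by the core laboratory rather than adjudicated by the CEC, and nothing gives the core laboratory a sizing judgement to make. In a single-arm study, a judgement left this open could be made knowing that the stent had moved.

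At stake is whether the observed MAE rate and its benchmark count the same events. Migration supplies 1.4 of the 5.6 points from which the 12.5% goal was set. The same definition applies to the secondary MAE endpoint, which is still being followed to 36 months.

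**Working it through.** **1. Reproduce the plan's safety design.** Inputs from SAP section 6.3: n = 193, goal 12.5%, expected rate 5.6%, one-sided alpha 0.025, pass if 15 or fewer events. With X binomial(193, p):

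- P(X ≤ 15 | p = 0.125) = 0.0249. The SAP states 0.0249.
- P(X ≤ 15 | p = 0.056) = 0.9233. The SAP states 0.9233.

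The stated design is correct.

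**2. How close the decision is.** The exact one-sided 97.5% upper limit is the 0.975 quantile of Beta(x + 1, n − x).

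- 15/193 = 7.8%, limit 12.49%: pass.
- 16/193 = 8.3%, limit 13.1%: fail.
- If all 200 implanted subjects are evaluable: 15/200 gives 12.07% (pass) and 16/200 gives 12.67% (fail).

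Near the boundary, one reclassified subject changes the conclusion.

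**3. Weight of migration in the benchmark.** The weighted averages in Appendix A Table IV are death 0.0, stent thrombosis 2.9, migration 1.4, pulmonary embolism 0.2 and major bleeding 1.1. They sum to 5.6, so migration is 1.4/5.6 = 25% of the expected rate. Only 13 rows of Table IV give a migration figure; the others are marked as not specified.

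**4. Illustration of the size condition.** Let f be the share of real migrations removed and m the migration rate. The documents do not give f, so it is an assumption shown over its full range. Set the true MAE rate, counting all migrations, at exactly 12.5%, where the chance of passing should be about 2.5%. Assume that removed subjects have no other MAE component. Then

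counted rate = 12.5% − f × m, and chance of passing = P(X ≤ 15 | 193, counted rate).

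With m = 1.4%:

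| f | Counted rate | Expected events removed (193 × f × m) | Chance of passing |
|---|---|---|---|
| 0% | 12.50% | 0 | 2.5% |
| 25% | 12.15% | 0.7 | 3.4% |
| 50% | 11.80% | 1.4 | 4.7% |
| 100% | 11.10% | 2.7 | 8.3% |

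As a check, m = 1.6% (Table XII, which includes migration beyond 30 days) gives 3.6%, 5.1% and 9.6% at f = 25%, 50% and 100%.

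**The case against.** **SAP Table 3 is the operative rule and has no size filter.** This is the strongest reply, and part of it stands. If the analysis followed Table 3 as written, sizing played no role, and neither document describes a step at which anyone judges it. But Table 3 uses the term migration without defining it for the MAE, and the SAP has no such definition elsewhere. A reader seeking one is sent to Appendix B, where the condition sits. The conflict is between two stated rules.

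**Large movements are still captured.** This is largely right. The delayed-migration endpoint has no size condition, and SAP section 10.3.2.4 counts positive findings cumulatively from day 0, so a move of more than 1 cm in the first month is reported there. Protocol section 12.2.4 also keeps migration reportable as an adverse event. However, the delayed-migration endpoint is descriptive and lies outside the 30-day test.

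**The benchmark is not firmly unrestricted.** This stands as a limit. The footnote applies only where the source series specified the matter, and it belongs to a 12-month table, not to the 30-day figure of 1.4%. The series' own definitions are not in the documents. What can be said is that the review states no sizing condition, not that every source series counted all migrations.

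**The pass probabilities are constructed.** Agreed. They pair a 12.5% true rate with a migration rate from a 5.6% population, and f is unknown. The index procedure required venography and IVUS before and after stenting, partly to aid sizing, so f = 100% is a ceiling and not a working estimate.

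**Deleting the condition leaves a second narrowing.** Also true. Appendix B still requires displacement beyond the intended treatment segment, which section 6.3.1 and Table 3 do not mention.

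**The primary test is already done.** This stands, and it shapes the fix: a tested endpoint should not be rewritten without saying so.

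**Conclusion.** The inconsistency is real and sits in the current text. Appendix B attaches an undefined size condition to the migration component of both MAE endpoints; the endpoint sections, SAP Table 3 and the literature review do not. Its only possible added effect is to remove post-procedure events, in the device's favour.

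Three stronger readings are tempting, and the documents support none of them.

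- *Real migrations were dropped from the primary safety result.* Nothing shows that any event was removed, and Table 3 would not remove one.
- *The safety test ran at a type I error of up to 8.3%.* That figure needs every migration to be in a stent judged undersized and every such subject to have no other MAE. The range of 2.5% to 8.3% shows sensitivity; it does not estimate the trial's error rate.
- *The 6.3.1 note supports leaving out undersized stents.* It mentions under-sizing only as a possible cause of movement at the index procedure.

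No stated figure in the sample-size calculation is wrong. The practical weight is at most about 2.7 expected events in 193 under the assumptions above, but the pass boundary turns on one. The passages should be reconciled and the all-migration count shown.

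**What to change.** 1. **MAE endpoints still followed to 36 months.** Remove *properly sized* from the Appendix B migration definition, so that on stent sizing it agrees with Protocol sections 6.3.1 and 6.3.2 and SAP Table 3. In the same edit, state whether displacement beyond the treatment segment is meant to be required, since those sections do not say.
2. **Completed 30-day primary safety endpoint.** Keep the tested result as it is. Beside it, report the MAE rate and the exact one-sided 97.5% upper limit counting every core-laboratory-confirmed post-procedure migration, whatever the stent sizing.
3. **Disclosure.** State whether any event was excluded on sizing, by whom and on what criterion. Give the properly-sized subset as a descriptive breakdown.

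The cost is a wording change and a re-count from existing core-laboratory data. If no event was excluded, the re-count confirms the result and settles the question. The downside is that the MAE rate may become slightly less favourable.

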## Appendix C CEAP Classification

The CEAP classification  is a method for evaluating venous disease of the leg based on clinical, etiologic, anatomic, and pathophysiologic data.

The CEAP system consists of two parts: classification and severity scoring:

### Classification

- C- clinical manifestation
- E- etiologic factors
- A- anatomic distribution
- P- pathophysiologic dysfunction

### Severity Scoring

1. Number of anatomic segments affected
2. Grading of signs and symptoms
3. Disability

### CLINICAL CLASSIFICATION

- C0: no visible or palpable signs of venous disease
- C1: telangiectasies or reticular veins
- C2: varicose veins
- C3: edema
- C4a: pigmentation and eczema
- C4b: lipodermatosclerosis and atrophie blanche
- C5: healed venous ulcer
- C6: active venous ulcer

S: symptoms including ache, pain, tightness, skin irritation, heaviness, muscle cramps, as well as other complaints attributable to venous dysfunction.

A: asymptomatic.

### ETIOLOGIC CLASSIFICATION

- Ec: congenital
- Ep: primary
- Es: secondary (postthrombotic)

### ANATOMIC CLASSIFICATION

- s: superficial veins
- p: perforator veins
- d: deep veins

## PATHOPHYSIOLOGIC CLASSIFICATION

### Basic CEAP:

- Pr: reflux
- Po: obstruction
- Pr,o: reflux and obstruction
- Pn: no venous pathophysiology identifiable

### Advanced CEAP:

Same as Basic with the addition that any of 18 named venous segments can be utilized as locators for venous pathology:

#### *Superficial veins:*

1. telangiectasies/reticular veins
2. GSV above knee
3. GSV below knee
4. SSV
5. Nonsaphenous veins

#### *Deep veins:*

6. IVC
7. Common iliac vein
8. Internal iliac vein
9. External iliac vein
10. Pelvic: gonadal, broad ligament veins, other
11. Common femoral vein
12. Deep femoral vein
13. Femoral vein
14. Popliteal vein
15. Crural: anterior tibial, posterior tibial, peroneal veins (all paired)
16. Muscular: gastrocnemial, soleal veins, other

#### *Perforating veins:*

17. Thigh
18. Calf

## Appendix D Villalta Score

The Villalta Score is a reliable and valid measure of Postthrombotic syndrome (PTS) in patients with previous, objectively confirmed deep vein thrombosis noting responsiveness to clinical change in PTS.

The Villalta score will categorize the severity of PTS.

Symptoms/clinical signs	None	Mild	Moderate	Severe
Symptoms				
Pain	0 points	1 point	2 points	3 points
Cramps	0 points	1 point	2 points	3 points
Heaviness	0 points	1 point	2 points	3 points
Paresthesia	0 points	1 point	2 points	3 points
Pruritus	0 points	1 point	2 points	3 points
Clinical signs				
Pretibial edema	0 points	1 point	2 points	3 points
Skin induration	0 points	1 point	2 points	3 points
Hyperpigmentation	0 points	1 point	2 points	3 points
Redness	0 points	1 point	2 points	3 points
Venous ectasia	0 points	1 point	2 points	3 points
Pain on calf compression	0 points	1 point	2 points	3 points
Venous ulcer	Absent			Present

A total score of 0 to 4 indicates no postthrombotic syndrome; score of  $\geq 5$  indicates PTS. PTS severity: total score of 5 to 9, mild PTS; score of 10 to 14, moderate PTS; and score of  $\geq 15$  or venous ulcer present, severe PTS.

## Appendix E Venous Clinical Severity Score (VCSS)

Venous disease severity measurement intended to evaluate the responses to changes in disease severity over time and in response to treatment.

	None: 0	Mild: 1	Moderate: 2	Severe: 3
Pain or other discomfort (i.e. aching, heaviness, fatigue, soreness, burning)  Presumes venous origin		Occasional pain or other discomfort (i.e. not restricting regular daily activities)	Daily pain or other discomfort (i.e. interfering with but not preventing regular daily activities)	Daily pain or discomfort (i.e., limits most regular daily activities)
Varicose Veins “Varicose” veins must be $\geq 3$ mm in diameter to qualify in the standing position		Few: scattered (i.e., isolated branch varicosities or clusters) Also includes corona phlebectatica (ankle flare)	Confined to calf or thigh	Involves calf and thigh
Venous Edema Presumes venous origin		Limited to foot and ankle area	Extends above ankle but below knee	Extends to knee and above
Skin Pigmentation Presumes venous origin  Does not include focal pigmentation over varicose veins or pigmentation due to other chronic diseases (i.e., vasculitis purpura)	None or focal	Limited to perimalleolar area	Diffuse over lower third of calf	Wider distribution above lower third of calf
Inflammation More than just recent pigmentation (i.e., erythema, cellulitis, venous eczema, dermatitis)		Limited to perimalleolar area	Diffuse over lower third of calf	Wider distribution above lower third of calf
Induration Presumes venous origin of secondary skin and subcutaneous changes (i.e., chronic edema with fibrosis, hypodermatitis)  Includes white atrophy and lipodermatosclerosis		Limited to perimalleolar area	Diffuse over lower third of calf	Wider distribution above lower third of calf

Active Ulcer Number	0	1	2	≥3
Active Ulcer Duration (longest active)	N/A	<3 mo	>3 mo but <1 y	Not healed for >1 y
Active Ulcer Size (largest active)	N/A	Diameter <2 cm	Diameter 2-6 cm	Diameter >6 cm
Use of Compression Therapy	0 Not used	1 Intermittent use of stockings	2 Wears stockings most days	3 Full compliance: stockings

